9.4.2 Operational Outcome Definition and Identification Process

All outcome variables will be provided by the obstetric HCP and/or pediatrician attending the birth. The HCP will be asked to describe any MCMs observed in the infant or fetus and will also be asked to report the gestational age and birth weight. These 2 variables will be used to calculate preterm birth (gestational age <37 weeks at birth) and LBW (birth weight <2500 g). A teratologist/geneticist will review all reported congenital anomalies and classify them using the CDC's MACDP system as specified in [Section 9.3.2](#). Additionally, the teratologist/geneticist will provide an opinion regarding the possible temporal association of the BEXSERO exposure to the development of observed defects. If additional information is needed to aid in classification or temporality assessment, the teratologist will request additional information using the targeted follow-up process outlined in [Section 9.4](#).

The SAC will meet periodically to review the data, discuss the MCM cases and their classification and temporality with the teratologist, and reach consensus on the coding and classification of MCMs and other primary endpoints.

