9.3.2 Outcome(s) of Interest

Major Congenital Malformation (MCM): The registry defines, classifies, and codes MCMs with criteria specified by CDC MACDP ([CDC, 2007](#)). Newborn and infant conditions that are not necessarily considered MCMs appear in the Exclusion List for the MACDP. These conditions may be included under certain circumstances by CDC criteria and will be considered “conditional defects” in the registry (e.g., skin tags, webbed toes, etc.). Please see the following link for a listing of all MACDP MCMs and conditions on the Exclusion List:

<http://www.cdc.gov/ncbddd/birthdefects/documents/macdpcode0807.pdf>.

The registry defines an MCM as any major structural or chromosomal defect or combination of 2 or more conditional defects in live-born infants, stillbirths, or fetal losses of any gestational age (including outcomes prior to 20 weeks' gestation or birth weight <500 g). This definition is consistent with, but not restricted to, the CDC MACDP definition. Clusters of conditional abnormalities (as defined by CDC MACDP) and data from aborted fetuses of less than 20 weeks' gestation, when available, will be included to increase sensitivity of monitoring. The MACDP includes conditional defects only if in the presence of a major defect. This registry will consider reports of 2 or more conditional defects as a defect case, to increase signal sensitivity and to capture instances where a combination of conditional events might constitute a major defect or syndrome.

The registry conforms to the CDC MACDP guidelines in disqualifying as defects those findings that are present in infants born at less than 36 weeks of gestation, and are attributable to prematurity itself, such as patent ductus arteriosus, patent foramen ovale, or inguinal hernias. The CDC MACDP classification does include chromosomal defects. Though vaccine exposure is not likely to contribute to a risk for chromosomal defects, the registry includes these defects to maintain this consistency with the CDC MACDP.

Live-born infants with only transient or infectious conditions or with biochemical abnormalities will be classified as being without reported MCMs unless there is a possibility that the condition reflects an unrecognized MCM. Detected and reported transient or infectious conditions or biochemical abnormalities in infants without reported MCMs and defects that are excluded by the CDC guidelines will be noted in an appendix in the registry reports.

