9.4.4 Advisory Committee(s)

An SAC will be established to oversee the scientific affairs of the registry, including its ongoing monitoring. The SAC will comprise recognized experts in the fields of teratology, epidemiology, maternal and fetal medicine, and therapeutic areas from government, academia, private practice, and GSK. The SAC will meet prior to each registry report to review the accumulated body of data from the registry, including review and classification of reported MCMs, and to carry out any actions required, including review and interpretation of interim data analyses and reports and publications of registry data. The SAC may meet on ad hoc occasions if indicated. In addition to the above activities, the SAC will design and implement strategies to heighten awareness of the registry.

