9.5 Study Size

The pregnancy registry is a PMC agreed upon with the CBER to commence enrolment on 31 January 2016 and to continue for a period of 3 years or pending CBER review and discussion of results with GSK. will submit a full study report to CBER by 31 May 2020.

The registry will prospectively enroll women with confirmed or possible (i.e. if the brand is unknown) exposure to BEXSERO 30 days prior to LMP or at any time during pregnancy. BEXSERO is not contraindicated during pregnancy, but should be used during pregnancy only if clearly needed. Under the current ACIP recommendations, the CDC estimates 350,000 individuals will be advised to receive a meningococcal B vaccine (MacNeil, 2015), of whom it is likely that a small proportion will be exposed during pregnancy. There are uncertainties regarding the degree of market penetration and vaccine uptake that will be achieved in at-risk groups. A recent US study of the safety of Cervarix[®] in pregnancy was terminated due to low accrual of subjects attributed to low uptake of the vaccine in the US (GSK, 2015). To account for this, and that the proportion of clinically recognized pregnancies that can be expected to result in a live birth is approximately 62% (Martin, 2015), a range of sample size estimates was considered, from a minimum of 5 to 150 live births.

It is likely that the majority of exposures (99%) will be the result of inadvertent exposure within 30 days prior to LMP or early in the first trimester before pregnancy status is known. If exposures occur later in pregnancy, results will be stratified by trimester of exposure, acknowledging that the power of stratified analyses to detect statistically significant differences will be limited by the sample size of each subgroup.

The expected low frequency of BEXSERO exposure in pregnancy will limit the statistical power of this study. As the sample size of the study increases, there will be a corresponding increase in the power of the study to detect increases in the prevalence of outcomes. The study will have greater power to detect prevalence increases for relatively common outcomes (with higher prevalence) but will have less power to for more uncommon outcomes, such as MCM.

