According to the CDC MACDP, the prevalence of MCMs for mothers <25 years of age in the US is 2.54% (Correa, 2007). According to the CDC National Vital Statistics System (NVSS), the prevalence of preterm birth and LBW for mothers <25 years of age are 11.71% and 8.50%, respectively (Martin, 2015).

The table below depicts sample sizes of 5, 20, 50, 100, and 150 live births and the associated effect sizes (i.e., the ratio of the registry-derived prevalence versus the reference prevalence) that would be detectable using a binomial distribution, a power of 80%, and a 1-sided Type I (false positive) error rate of 5% (Altman, 1991). For example, with a sample size of 100 live births, the study will have 80% power to detect a 1.79-fold

increase in the prevalence of preterm birth compared with the reference of 11.71% (population prevalence). In other words, if the registry-derived prevalence estimate is at least 1.79 times higher than the reference prevalence of preterm birth, the 1-sided 95% confidence interval for the estimate will exclude 11.71% (i.e., will lie above 11.71%), with a probability of 80%.

Table 9.5-1 Detectable effect size assuming 80% power

Sample size (N of live births)	Effect size (ratio of the registry-derived prevalence versus the reference prevalence for mothers <25 years of age)		
	MCM [reference = 2.54%]	PTB [reference = 11.71%]	LBW [reference = 8.50%]
5	19.30	5.75	7.92
20	7.95	3.13	3.69
50	4.23	2.24	2.59
100	3.07	1.79	1.96
150	2.66	1.63	1.82

Abbreviations: LBW = low birth weight; MCM = major congenital malformations; PTB = preterm birth.

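### MCM codes are finalised by reviewers who also know and discuss vaccination timing, with no masking to date and no record of code changes, leaving the few discretionary calls open to avoidable influence

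*Combined protocol and SAP*

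**What the plan says.** **Who codes.** Section 9.4.2 has a teratologist/geneticist review every reported anomaly and classify it by the MACDP system as set out in 9.3.2. The same person also gives an opinion on whether the defect is temporally associated with BEXSERO. The SAC then meets periodically to "discuss the MCM cases and their classification and temporality with the teratologist, and reach consensus on the coding and classification of MCMs". Section 9.4 repeats this arrangement.

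**What the SAC sees.** Section 9.4.4 has the SAC meet before each registry report to "review the accumulated body of data from the registry, including review and classification of reported MCMs", and to interpret interim analyses.

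**Where judgement enters.** Section 9.3.2 treats live-born infants with only transient, infectious or biochemical findings as having no MCM, "unless there is a possibility that the condition reflects an unrecognized MCM". It also disqualifies findings in infants born before 36 weeks that are attributable to prematurity.

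**What counts.** Section 9.7.3 admits a case to the primary analysis if it meets MACDP criteria or has two or more conditional defects. Its formula divides affected live births and affected losses at 20 weeks or later by live births. Vaccination timing appears only as a stratifying variable, not as a condition for being counted.

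**What stays visible.** Section 9.7.3 lists single minor defects in the report. Section 9.3.2 places transient or biochemical findings, and defects excluded under the CDC rules, in an appendix.

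**The concern.** The registry's MCM prevalence is compared with an external surveillance rate whose cases are counted without reference to any vaccination date. For a fair comparison, the registry's codes should also be assigned without that information. As planned, the person who assigns the code also judges temporality, and the committee that finalises the code does so in the same discussion, with accumulated data in view. Where the criteria leave discretion, knowing how the vaccination date sits against the defect could sway the call, in or out.

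MCM counts will be small, so a single case can decide whether the one-sided 95% bound excludes the reference. The Rule of Three in Section 9.4.5 also turns on one case, the third similar defect. Without a locked first code or a change log, a reader of a near-threshold result cannot see which codes were changed in discussion, or why.

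**Working it through.** **Inputs from Section 9.5.** The MCM reference is p0 = 2.54%. The test is a one-sample binomial at one-sided 5% with 80% power, for "sample sizes of 5, 20, 50, 100, and 150 live births". The tabled MCM ratios R are 19.30, 7.95, 4.23, 3.07 and 2.66. The signal criterion is a one-sided 95% lower bound above the reference. Section 9.5 illustrates it for preterm birth, and I apply it to MCM.

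**Step 1: reproduce the table.** Take k as the smallest count with P(X ≥ k | n, p0) ≤ 0.05, then solve P(X ≥ k | n, p1) = 0.80 and report p1/p0. The exact binomial gives 19.30, 7.95, 4.23, 3.07 and 2.66, matching Table 9.5-1.

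**Step 2: when one case decides.** Exact (Clopper-Pearson) lower bounds at k−1 and at k cases:

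| n | k | bound at k−1 | bound at k |
|---|---|---|---|
| 5 | 2 | 1.02% | 7.64% |
| 20 | 3 | 1.81% | 4.22% |
| 50 | 4 | 1.66% | 2.78% |
| 100 | 6 | 1.99% | 2.64% |
| 150 | 8 | 2.21% | 2.68% |

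The bound crosses 2.54% between k−1 and k at every size. One recoded case matters there and nowhere else.

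**Step 3: worst case, exactly one case moved in every study.** With p1 = R × 0.0254 (for example 4.23 × 0.0254 = 0.1074 at n = 50):

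- one true case always coded out: power = P(X ≥ k+1 | n, p1)
- one case always coded in, no true effect: false-signal chance = P(X ≥ k−1 | n, p0)

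| n | power as planned | one coded out | false signal as planned | one coded in |
|---|---|---|---|---|
| 5 | 80% | 48% | 0.6% | 12.1% |
| 20 | 80% | 60% | 1.4% | 9.1% |
| 50 | 80% | 63% | 3.8% | 13.4% |
| 100 | 80% | 67% | 4.3% | 11.2% |
| 150 | 80% | 69% | 3.9% | 8.9% |

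The power loss equals the chance that the count falls exactly on k: 0.799 − 0.635 = 0.164 at n = 50, 0.801 − 0.671 = 0.130 at 100, and 0.801 − 0.690 = 0.111 at 150.

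**Step 4: how extreme that is.** With no effect, expected MCMs are 50 × 0.0254 = 1.27, 100 × 0.0254 = 2.54 and 150 × 0.0254 = 3.81. Always adding one case therefore inflates the expected count by 79%, 39% and 26%.

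**Step 5: smaller assumed influence.** The documents give no rate of swayed codes, so 2% and 5% are assumptions. Power uses p1 × (1 − f), and the false-signal chance uses p0 × (1 + f).

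| f | power, n = 50 / 100 / 150 | false signal, n = 50 / 100 / 150 |
|---|---|---|
| 2% | 79 / 78 / 78% | 4.0 / 4.6 / 4.2% |
| 5% | 76 / 76 / 75% | 4.4 / 5.2 / 4.9% |

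**The case against.** **Coding already comes first, under written criteria.** Section 9.4.2 describes MACDP coding before the temporality opinion. Section 9.3.2 bounds much of the discretion: conditional defects count at two or more, and the prematurity rule has a gestational limit and named examples. This stands in part. The openly discretionary call is the unrecognized-MCM clause, followed by attribution to prematurity. However, the order of description does not require the first code to be recorded, masked or kept.

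**Temporality is not an inclusion criterion.** This is correct. A reader might infer that cases judged unrelated in time are dropped from the numerator, but 9.7.3 contains no such rule. Any influence would come through judgement.

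**Downgraded cases stay visible.** A reader might infer that the bias could never be detected. The listings required by 9.3.2 and 9.7.3 contradict that for many cases coded out. They do not show that a code was changed, or why.

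**The date may carry little information.** Section 9.5 expects 99% of exposures to be "inadvertent exposure within 30 days prior to LMP or early in the first trimester before pregnancy status is known". That window pools vaccination before LMP with vaccination in the first trimester, where 9.7.3 places the origin of most structural defects, so timing can differ in meaning within it. A reader might go further and infer that the date settles temporality in nearly every case. No section sets such a criterion, so that reading is not supported. The effect on trimester strata is likewise small if 99% fall in this window.

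**Surveillance needs cumulative review.** Section 9.4.5 requires the teratologist and SAC to review MCMs individually and cumulatively on an ongoing basis. This stands: masking the SAC to running counts would conflict with that duty and is not proposed.

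**The registry is descriptive.** Section 9.7.1 says so. This limits the consequence, but the comparison with the reference remains the planned reading of the MCM result.

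**Conclusion.** The point holds as a minor, inexpensive improvement to outcome assessment. It is not an error or contradiction in the plan. Coding and temporality share the same reviewers and the same discussion, and no section of the document masks the date, locks the first code or records changes. Since the numerator does not use timing, hiding it during coding loses nothing.

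The documents show neither that bias occurs nor which way it would run. The losses in Step 3 (power down to 63%, 67% and 69%; false-signal chance up to 13%, 11% and 9%, for 50, 100 and 150 live births) are an upper illustration. They assume one case moved the same way in every study, and they should not be read as expected effects. Under the assumed 2% to 5% influence, power stays at 75% to 79% and the false-signal chance at 4.0% to 5.2%. All figures rest on the exact binomial rule behind Table 9.5-1, and on applying to MCM the signal criterion that 9.5 illustrates for preterm birth.

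**What to change.** Amend Sections 9.4.2 and 9.4.4 as follows:

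1. The teratologist records and locks the MACDP code from a case summary prepared by the registry coordination center. The summary omits vaccination date and trimester of exposure. It keeps gestational age at birth, which the prematurity rule needs.
2. The date is then revealed for the temporality opinion and for SAC and cumulative review, which proceed as in 9.4.5.
3. Any SAC change to the locked code is logged with its reason.
4. MCM prevalence is reported under both the locked and the consensus codes.

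The cost is slightly more preparation per case and one extra sensitivity line in the report. No additional reviewer or data collection is needed. Masking to exposure itself is not possible, because every woman in the primary analysis was vaccinated.

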9.4.3 Operational Variable(s) Definition

As is indicated in [Section 9.4](#), for women who self-enroll in the registry, maternal characteristics will be provided by the pregnant woman at registry enrollment. After the

woman provides consent and medical release for her HCP(s) to provide data, the obstetric HCP will provide prenatal data (LMP, EDD, and CEDD), prenatal test data (test, date of test, and result), obstetrical history (previous pregnancies, live births, stillbirths, SABs, IABs, births with congenital malformations, and family history of congenital malformations), concurrent medical conditions, concomitant medications and vaccines, and alcohol, tobacco, and illicit drug use. At pregnancy outcome, the obstetric HCP will provide pregnancy outcomes data (live birth, stillbirth, SAB, IAB, or ectopic or molar pregnancy) and infant outcome (gestational age, birth weight, and sex).

If HCPs provide de-identified data to the registry, they will provide required data on maternal characteristics, prenatal data, obstetrical data, and pregnancy outcome data.

9.4.4 Advisory Committee(s)

An SAC will be established to oversee the scientific affairs of the registry, including its ongoing monitoring. The SAC will comprise recognized experts in the fields of teratology, epidemiology, maternal and fetal medicine, and therapeutic areas from government, academia, private practice, and GSK. The SAC will meet prior to each registry report to review the accumulated body of data from the registry, including review and classification of reported MCMs, and to carry out any actions required, including review and interpretation of interim data analyses and reports and publications of registry data. The SAC may meet on ad hoc occasions if indicated. In addition to the above activities, the SAC will design and implement strategies to heighten awareness of the registry.

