3.4 Advisory Committee

The Scientific Advisory Committee will provide an independent review of registry data and will include specialists from appropriate fields such as obstetrics, pediatrics, clinical research, genetics, epidemiology, and teratology from academic institutions, private practice, and/or government agencies.

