and 2 during gestation) at a dose equivalent to the absolute human dose or 15 times the human dose on a body weight basis (4 kg in rabbits and 60 kg in humans). This study was designed to comply with FDA guidance on the testing of the developmental toxicity of vaccines, and according to International Conference on Harmonisation (ICH) Harmonised Tripartite Guideline (ICH, 1996) (stages A through E of the reproductive process, with the exception of determination of effects on estrous cycle). Evaluation of the maternal animals, their developing fetuses, and offspring for up to 4 weeks after birth demonstrated that BEXSERO was not a reproductive or developmental toxicant (Ching-Long, 2014). The vaccine was immunogenic in the maternal animals; circulating antibodies were detected in their fetuses and persisted in offspring through day 29 of lactation (ELISA and SBA with rabbit complement).

BEXSERO is not contraindicated during pregnancy, but according to the vaccine label, BEXSERO should be used during pregnancy only if clearly needed. Inadvertent exposure within 30 days prior to last menstrual period (LMP) or early in the first trimester (before pregnancy status is known) might be expected to occur because the age group targeted for the vaccine includes young women of reproductive potential. The BEXSERO Pregnancy Registry is established to meet a Center for Biologics Evaluation and Research (CBER) post-marketing commitment (PMC) and is designed to collect prospective data on pregnancy outcomes among women immunized with the BEXSERO vaccine within 30 days prior to LMP or at any time during pregnancy. The registry will add to the current clinical experience with BEXSERO, supplementing existing data from animal toxicology studies and human exposure data. Pregnancy data will be collected at registry enrollment and, where accessible, at the end of the second trimester of pregnancy, and at pregnancy outcome for both mother and infant. GSK will sponsor the registry in consultation with specialists from appropriate fields such as obstetrics, pediatrics, clinical research, genetics, epidemiology, and teratology from academic institutions, private practice, and/or government agencies. These individuals constitute the Scientific Advisory Committee (SAC) and will provide an independent review of registry data.

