10.5 Does the plan describe methods for handling missing data?				9.7
10.6 Is sample size and/or statistical power estimated?				9.5

Comments:

--

Section 11: Data management and quality control	Yes	No	N/A	Section Number
11.1 Does the protocol provide information on data storage? (e.g. software and IT environment, database maintenance and anti-fraud protection, archiving)				9.8.2
11.2 Are methods of quality assurance described?				9.8
11.3 Is there a system in place for independent review of study results?				3.4

Comments:

--

Section 12: Limitations	Yes	No	N/A	Section Number
12.1 Does the protocol discuss the impact on the study results of:				
12.1.1 Selection bias?				9.9
12.1.2 Information bias?				9.9
12.1.3 Residual/unmeasured confounding?				9.9
(e.g. anticipated direction and magnitude of such biases, validation sub-study, use of validation and external data, analytical methods)				
12.2 Does the protocol discuss study feasibility? (e.g. study size, anticipated exposure, duration of follow-up in a cohort study, patient recruitment)				9.5

Comments:

--

Section 13: Ethical issues	Yes	No	N/A	Section Number
13.1 Have requirements of Ethics Committee/ Institutional Review Board been described?				10.2 10.3
13.2 Has any outcome of an ethical review procedure been addressed?				10.3
13.3 Have data protection requirements been described?				10

Comments:

--

Section 14: Amendments and deviations	Yes	No	N/A	Section Number

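### The advisory committee is described as independent, but Section 9.4.4 seats sponsor members on it and no rule keeps them out of the consensus on major congenital malformation (MCM) classification

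*Combined protocol and SAP*

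**What the plan says.** All the text at issue is in the current combined protocol and SAP.

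- **Section 3.4:** "The Scientific Advisory Committee will provide an independent review of registry data". Its specialists come "from academic institutions, private practice, and/or government agencies". The sponsor is not listed.
- **Section 7** (the abstract says the same): after naming outside specialists whom the sponsor consults, it states "These individuals constitute the Scientific Advisory Committee (SAC) and will provide an independent review of registry data".
- **Appendix 2, ENCePP checklist item 11.3:** the question "Is there a system in place for independent review of study results" is answered Yes, with a pointer to Section 3.4.
- **Section 9.4.4:** SAC members are experts "from government, academia, private practice, and GSK". Before each registry report the committee reviews the accumulated data, "including review and classification of reported MCMs".
- **Section 9.4.2:** "A teratologist/geneticist will review all reported congenital anomalies and classify them" under the MACDP system (the CDC's Atlanta birth defects surveillance program). The SAC then discusses the cases with the teratologist to "reach consensus on the coding and classification of MCMs and other primary endpoints". Section 9.4 places the teratologist on the SAC.
- **Section 12.2:** manuscripts are to be prepared by the SAC independently, and the sponsor may see them and comment before submission.

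The documents do not say how many sponsor members there are or what share of the committee they form. They give no rule on voting, recusal or observer status.

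**The concern.** Section 9.4.4 is the operative section on the committee, and it gives the sponsor seats on a body that other sections present as external. That body is more than advisory: its consensus fixes which reported anomalies count as MCMs, and so which enter the numerator defined in Section 9.7.3.

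Two features of the design make this matter. First, the registry has one arm and is compared with a published external prevalence, so no concurrent group is classified by the same people in which a shared tendency could cancel. Second, Section 9.3.2 leaves room for judgement. Someone must decide whether conditional defects combine into a case, whether a finding is due to prematurity, and whether a transient or biochemical condition might reflect an unrecognized MCM.

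A regulator reading Section 3.4 or checklist item 11.3 would take it that people outside the sponsor carry out the review. The plan as written does not guarantee that.

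**Working it through.** **Step 1. Set the passages side by side.**

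| Place | Who sits on the SAC | Described as independent? |
|---|---|---|
| Abstract, Section 7 | Outside specialists, who constitute the SAC | Yes |
| Section 3.4 | Will include outside specialists (not exhaustive wording) | Yes |
| Appendix 2, item 11.3 | Cites Section 3.4 | Yes |
| Section 9.4.4 | Government, academia, private practice and the sponsor | Not stated |

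The direct conflict is between the abstract and Section 7 on one side and Section 9.4.4 on the other. Section 3.4 alone could be read as compatible with further members.

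**Step 2. Is there a separate layer of adjudication?** The teratologist classifies first, but sits on the SAC, and the SAC's consensus follows. No body outside the SAC settles MCM status.

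**Step 3. Which outcomes are exposed to judgement?** Section 9.4.2 calculates preterm birth and low birth weight from reported gestational age and birth weight, with cut-offs of 37 weeks and 2500 g. Little is left for a committee to decide. The issue is essentially MCM, one of three primary outcomes.

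**Step 4. How much can one case matter?** Inputs from Section 9.5 are the reference MCM prevalence of 2.54%, a one-sided error rate of 5%, 80% power, and 5 to 150 live births.

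The plan's own figures come first. Find the smallest r with P(X ≥ r | n, 0.0254) ≤ 0.05, solve P(X ≥ r | n, p1) = 0.80, and divide p1 by 0.0254. For n = 5, 20, 50, 100 and 150 this gives 19.30, 7.95, 4.23, 3.07 and 2.66, which is the MCM column of Table 9.5-1. The preterm birth and low birth weight columns also reproduce to two decimals.

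Next, the exact (Clopper-Pearson) one-sided 95% lower limit at r cases and at one fewer. Expected cases are 0.0254 × n, and one case moves the estimate by 1/n.

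| Live births | Expected cases | r | Lower limit at r | Lower limit at r − 1 | One case (percentage points) |
|---|---|---|---|---|---|
| 5 | 0.13 | 2 | 7.64% | 1.02% | 20 |
| 20 | 0.51 | 3 | 4.22% | 1.81% | 5 |
| 50 | 1.27 | 4 | 2.78% | 1.66% | 2.0 |
| 100 | 2.54 | 6 | 2.64% | 1.99% | 1.0 |
| 150 | 3.81 | 8 | 2.68% | 2.21% | 0.67 |

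At r cases the limit lies above 2.54% in every row; with one case fewer it lies below.

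**Step 5. How likely is the count to stand exactly at r?** This is the binomial probability P(X = r). If the true prevalence is 2.54%, it is 2.9%, 2.9% and 2.4% at 50, 100 and 150 live births. At the plan's own detectable effects (true prevalence 4.23, 3.07 and 2.66 times 2.54%), it is 16%, 13% and 11%. In those scenarios the loss of one case would reduce the power to exclude 2.54% from about 80% to 64%, 67% and 69%.

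**The case against.** Several points on the other side stand.

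- **Review, not adjudication.** The plan promises an independent review of registry data and nowhere independent adjudication of endpoints. A reader might infer that a promised adjudication of the primary safety endpoint has been broken. The documents do not support that: the word is review, and MCM is one of three primary outcomes. What remains is that classification is part of the review so described.
- **Influence is not documented.** Nothing shows that sponsor members vote or outnumber others. The MACDP criteria and the teratologist's first classification limit discretion.
- **The interval is not the signal rule.** A reader might infer that one reclassified case decides whether a signal is declared. Section 9.4.5 relies instead on individual and cumulative case review, the Rule of Three for similar MCMs, and a threshold for action that depends on certainty about the cases. The registry calls itself primarily descriptive. The effect in Step 4 is on the reported interval, and only when the count is at the boundary.
- **Much stays visible.** The MCM definition is broader than MACDP's. Single minor defects are listed (Section 9.7.3), and excluded or transient conditions go in a report appendix (Section 9.3.2). Section 11 treats congenital anomalies as serious events, and annual reports go to CBER. A case left out of the numerator would in large part still be seen, which limits the harm but does not reconcile the text.
- **Exposure timing.** Because the SAC discusses classification and temporality together, a reader might ask for vaccination dates to be masked. Every case in the primary population is exposed, and Section 9.5 expects 99% of exposures just before or early in pregnancy. Masking would gain little and would require case files prepared without dates.

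**Conclusion.** The point holds as an unsecured safeguard. Outside specialists are said to make up the SAC and to review independently, yet Section 9.4.4 adds sponsor members to the committee that settles MCM status, without any limit on their part in it. Biased classification is not shown and should not be alleged.

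The size is conditional. At boundary counts of 4/50, 6/100 or 8/150, one classification determines whether the one-sided 95% interval excludes 2.54%. The chance of standing exactly there is 2.4% to 2.9% if the true prevalence equals the reference, and 11% to 16% at the plan's detectable effects. These figures assume exact binomial limits, the stated 2.54% reference, and cases counted as a proportion of live births. They measure how sensitive the result is to a single decision, not how likely a wrong decision is.

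The change is worth making because the comparison is single-arm, MCM counts will be few, and the remedy costs almost nothing.

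**What to change.** In Sections 9.4.2 and 9.4.4, state that sponsor members of the SAC are non-voting and recused from the consensus on classification of MCMs and other primary endpoints, and that they may answer questions. Align Section 3.4, the abstract, Section 7 and checklist item 11.3 with that statement, and check that Section 12.2 still describes manuscript preparation correctly.

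If the sponsor prefers its members to take full part, remove the word independent wherever it describes the SAC, correct the answer to item 11.3, and disclose the sponsor's role in classification in the protocol and in registry reports. That resolves the contradiction but gives less protection.

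The cost is wording in the protocol and in any SAC charter, with no extra assessors or data. The downside is that sponsor experts do not vote on classification. No masking of exposure timing is needed.
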